2.2.1.4. Clinical Experience

AGN-242428 delivered orally in support of a systemic treatment for psoriasis has been evaluated in 4 clinical trials with administration as single ascending doses (SAD) to 40 healthy volunteers (VTP-43742-001); administration once daily for 10 consecutive days to 30 healthy volunteers (VTP-43742-002 Part 1); administration once daily for 28 consecutive days to 29 patients with moderate to severe plaque psoriasis (VTP-43742-002 Part 2); and administration once daily for up to 12 weeks to 17 patients with moderate to severe plaque psoriasis (1957-201-001). The fourth trial was a single dose study comparing the relative bioavailability of 2 oral formulations of AGN-242428 (VTP-43742-003). More details are available in the AGN-242428 investigator's brochure.

In past assessment of AGN-242428 administered orally to participants with psoriasis (Allergan Study 1957-201-001), 4 study participants met the stopping criteria for liver function test (LFT) elevations (alanine aminotransferase [ALT] and/or aspartate aminotransferase [AST] were at or above $5 \times \text{upper limit}$ of normal [ULN]). Elevated LFT was found for 1 participant receiving 225 mg, 1 participant receiving 350 mg, and 2 participants receiving 450 mg AGN-242428. The earliest finding of elevated LFT was observed following 4 weeks of daily treatment with 450 mg of AGN-242428. There were no cases with associated serious adverse events (SAEs), and there were no combination cases (transaminases $\geq 3 \times \text{ULN} + \text{total bilirubin} \geq 2 \times \text{ULN}$) as all participants with elevated transaminases had total bilirubin values that were within normal limits. All 4 participants were asymptomatic and lab abnormalities resolved upon treatment discontinuation.

[figure not shown]

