9.4.2.1. Adverse Events

For each stage, the Medical Dictionary for Regulatory Activities (MedDRA) nomenclature will be used to code AEs.

An AE will be considered a treatment-emergent AE (TEAE) if either of the following apply:

- The AE began on or after the first dose of study intervention.
- The AE was present before the date of the first dose of study intervention but increased in intensity or became serious on or after the date of the first dose of study intervention.

An AE will be considered a treatment-emergent SAE (TESAE) if it is a TEAE that additionally meets any SAE criteria.

An AE that occurs after the Exit or Early Termination visit will not be counted as a TEAE.

The number and percentage of participants reporting TEAEs in each study intervention group will be tabulated by:

- 1) System Organ Class and Preferred Term
- 2) System Organ Class, Preferred Term, and severity

The number and percentage of participants reporting TEAEs and TESAEs will be tabulated separately by study intervention.

If more than 1 AE is coded to the same preferred term for the same participant, the participant will be counted only once for that preferred term using the most severe and most related occurrence for the summarizations by intensity and by relationship to study intervention.

Summary tables will be provided for participants with SAEs regardless of causality and participants with AEs leading to discontinuation.

The definitions of an AE and SAE can be found in Appendix 3.

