9.4.2.7. Biomicroscopy

For each stage, cup/disc ratio will be reported using 0.0 to 1.0 scale according to an Armaly chart provided by the sponsor. All data will be listed. No summary statistics will be provided.

For each stage, the number of participants with ophthalmoscopy findings of at least 2-grade severity increase from baseline will be generated for each MedDRA preferred terms at each postbaseline visit by study intervention for each eye. For findings under other pathology which are not associated with a severity grade, a status change from absent to present will be treated as a 2-grade increase in the analysis.

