AESI	Overall summary by cohort and study intervention group and by SOC and PT ^a	Categorical descriptives ¹ Supportive data listing

^a Create summary tables only if at least 5 participants reported SAE, AEs leading to study discontinuation or AESI.

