5.6.2.1. Adverse Events of Special Interest

Any report of the following AESIs will be provided in a listing. A summary table will be created only if there are reports by at least 5 participants.

Safety Statistical Analysis Plan 2012-201-005 [Stage 1]

Table 5-5 Adverse Events of Special Interest

Preferred Term (PT)	PT Code
Aspartate aminotransferase increased	10003481
Alanine aminotransferase increased	10001551
Blood bilirubin increased	10005364
Blood alkaline phosphatase increased	10059570

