5.6.3.9. Dilated Fundus Examination

Lens, vitreous, fundus, and optic nerve will be evaluated for pathology. If pathology is present, it will be recorded.

Cup/disc ratio will be reported using 0.0 to 1.0 scale according to an Armaly chart. Lens status will be assessed as phakic, pseudophakic, or aphakic. Cataract assessment for presence and severity of nuclear, cortical and posterior subcapsular cataract lens opacities will be evaluated. Each type of cataract severity and change from baseline will be evaluated. These data will be presented as listings only.

Table 5-15 Dilated Fundus Examination

Parameter	Description	Timing	Methodology
Dilated Fundus Examination	Listing for the following data: Cup/disc ratio Lens status Cataract assessment	Treatment period	Listing

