6.2. Appendix 2: Changes to Protocol-planned Analyses

There are no changes from the protocol-planned analyses.

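### The Stage 1 SAP makes the SAE and discontinuation tables conditional on 5 participants and drops the protocol's 2-grade eye-finding count, while declaring no changes from the protocol

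*SAP*

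**What the plan says.** **Protocol.** Section 9.4.2.1 (Adverse Events) commits to this: "Summary tables will be provided for participants with SAEs regardless of causality and participants with AEs leading to discontinuation". It sets no threshold and does not confine the promise to one stage. Section 9.4.2.7 (Biomicroscopy) says that, for each stage, "the number of participants with ophthalmoscopy findings of at least 2-grade severity increase from baseline will be generated", by preferred term, postbaseline visit, study intervention and eye. An ungraded finding that goes from absent to present counts as a 2-grade increase.

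**Stage 1 SAP.** Table 5-4 plans SOC/PT tables for TESAEs, for TEAEs leading to discontinuation and for AESIs. All three rows carry footnote a: "Create summary tables only if at least 5 participants reported SAE, AEs leading to study discontinuation or AESI". Section 5.6.2.1 repeats the rule for AESIs: "A summary table will be created only if there are reports by at least 5 participants". Section 5.6.3.8 counts slit-lamp findings with any increase in severity at one or more visits. Section 5.6.3.9 says of cup/disc ratio, lens status and cataract grading: "These data will be presented as listings only". It plans no summary of vitreous, fundus or optic nerve pathology. Section 6.2 (Appendix 2) states: "There are no changes from the protocol-planned analyses".

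**Stage 2 SAP.** Section 9.2.2 has an AESI line in the AE overview. Sections 9.2.4 and 9.2.5 tabulate SAEs, AEs leading to study drug discontinuation and AESIs with no minimum count. Section 9.8 plans the 2-grade count for biomicroscopy by visit and eye, and treats ophthalmoscopy similarly.

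**The concern.** Safety and tolerability are a primary objective of Stage 1, and dilated fundus examination and slit-lamp biomicroscopy are among its primary variables. Two summaries that the protocol promises are therefore either conditional or missing, and the section meant to disclose departures says there are none. A reader of the Stage 1 report could not tell whether a missing SAE table means no events, or one to four participants with events. The planned eye-finding counts would also differ between stages of the same study.

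**Working it through.** **1. Stage 1 size.** Each cohort has 9 + 9 + 3 + 3 = 24 participants, and up to 3 × 24 = 72 are planned. This matches the protocol. Stage 1 safety data are descriptive only, so no power calculation applies.

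**2. What the threshold means.** Footnote a does not say whether the 5 are counted per arm, per cohort or over the stage. Nor does it say whether they are counted per event category or over the three categories together. For a single category:

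| Counting unit | n | Share needed for a table (5/n) | Largest share with no table (4/n) |
|---|---|---|---|
| Vehicle arm, one cohort | 3 | cannot be reached | 3/3 = 100% |
| Active arm, one cohort | 9 | 55.6% | 44.4% |
| One cohort | 24 | 20.8% | 16.7% |
| Two cohorts | 48 | 10.4% | 8.3% |
| Three cohorts | 72 | 6.9% | 5.6% |

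The rule thus ranges from mild to nearly prohibitive, depending on a unit that the SAP leaves open.

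**3. Protocol against Stage 1 SAP.**

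| Output | Protocol | Stage 1 SAP |
|---|---|---|
| SAE summary table | Promised (9.4.2.1) | SOC/PT table only from 5 participants; by-arm total kept in overview |
| Discontinuation summary table | Promised (9.4.2.1) | Same |
| Ophthalmoscopy, at least 2 grades | Promised for each stage (9.4.2.7) | No count; listings |
| AESI table | Not promised in section 9 | Only from 5 participants; no overview row |
| Declared changes | – | None (6.2) |

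**4. Eye findings.** Section 9.4.2.7 is headed Biomicroscopy, but its sentence names ophthalmoscopy. On either reading the promised count is missing. If it means the dilated examination, Stage 1 has listings only. If it also means the slit lamp, Stage 1 uses another cut-off and pools visits. The 2-grade count cannot be recovered from the count of any increase: everyone who worsens by 2 grades is in it, mixed with smaller changes.

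**5. What remains below 5 participants.** The overall AE summary in Table 5-4 carries no footnote. It gives TESAEs, treatment-related TESAEs, TEAEs leading to study discontinuation and deaths by cohort and arm. The tables of TEAEs by SOC/PT, by severity and by relationship are also unconditional. They would include the four liver-related preferred terms that define AESIs in Table 5-5. ALT and AST above 3 × ULN are tabulated by cohort and arm in the PCS table (5.6.3.1, Table 6-5). TEAEs, TESAEs, discontinuations, deaths, AESIs and potential Hy's Law cases are listed. What is lost is the SOC/PT breakdown of SAEs and discontinuations, and a by-arm count of participants with any AESI. That count cannot be obtained by adding preferred-term rows, because one participant may appear in several.

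**The case against.** The strongest defence is that little information is lost. Step 5 shows that by-arm totals for SAEs and discontinuations, the liver terms and the transaminase PCS counts all survive, with full listings. With arms of 9 and 3, a listing may be as readable as a sparse table. The protocol's statistics section promises no AESI table. For the slit lamp, counting any increase is the more sensitive choice, and listing cup/disc ratio without summary statistics is what the protocol asks for. All of this stands, and it limits the consequence. It does not explain why promised tables became conditional, why the ophthalmoscopy count disappeared, or why Appendix 2 reports no change.

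A reader might infer more: that a liver signal as large as the oral one could go untabulated. In the oral psoriasis study of AGN-242428, "4 study participants met the stopping criteria for liver function test (LFT) elevations", the study having involved "administration once daily for up to 12 weeks to 17 patients", and 4 is just under 5. The documents do not support that inference. Such events would still be counted by arm in the TEAE and PCS tables. The dedicated AESI table is built on preferred terms, so it would not isolate cases at or above 5 × ULN even if produced. The oral rate also transfers poorly: the earliest elevation came after 4 weeks, whereas Stage 1 dosing ends on Day 15, and protocol 2.2.1.4 puts the highest ocular daily dose 625 times below the lowest oral dose with elevations (225 / 0.36 = 625).

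A reader might also infer that the rule hides by-arm SAE and discontinuation rates, or distorts the choice of dose and compound for Stage 2. The overview table answers the first. On the second, cohort progression follows DMC review of safety data (protocol 10.1.11), and protocol 9.5 says that the interim results are not needed to enter Stage 2.

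**Conclusion.** The point holds as an undeclared departure from the protocol in the reporting of primary safety variables. Two promised tables are made conditional on an undefined count of 5, which is anywhere from 6.9% of the stage to 56% of an active arm. The promised 2-grade count is absent. The AESI gap is a weakness in the SAP rather than a breach of the protocol. The harm is to completeness, traceability and comparability of the planned counts between stages. Nothing shows that a signal would be missed or that a Stage 2 decision was affected.

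One assumption: the Stage 1 SAP was written against protocol Amendment 2, and the protocol available is Amendment 3. The visible amendment log shows no change to 9.4.2.1 or 9.4.2.7, but part of the log is not available.

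**What to change.** - Delete the 5-participant condition from Table 5-4 footnote a and from section 5.6.2.1. Tabulate TESAEs, TEAEs leading to discontinuation and AESIs by cohort and arm with denominators, whatever the count.
- Add an AESI row to the overall AE summary, as in Stage 2 SAP 9.2.2.
- Add the count of participants with at least 2-grade worsening by arm, visit and eye, for ophthalmoscopy and slit lamp. Keep the count of any increase as supportive.
- Correct Appendix 2 to declare and justify any departure that remains. If a threshold is kept, state its counting unit.

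Stage 2 SAP section 10.0 records that Stage 1 has been locked, unmasked and analysed, so the added tables should be labelled supplementary. The cost is small: a few short tables from data already collected, plus SAP wording. The Stage 1 schedule has one postbaseline fundus examination (Visit 5 or Early Termination) and three scheduled postbaseline slit-lamp visits (Visits 3, 4 and 5).

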5.6.2.1. Adverse Events of Special Interest

Any report of the following AESIs will be provided in a listing. A summary table will be created only if there are reports by at least 5 participants.

Safety Statistical Analysis Plan 2012-201-005 [Stage 1]

Table 5-5 Adverse Events of Special Interest

Preferred Term (PT)	PT Code
Aspartate aminotransferase increased	10003481
Alanine aminotransferase increased	10001551
Blood bilirubin increased	10005364
Blood alkaline phosphatase increased	10059570

5.6.3. Additional Safety Assessments

5.6.3.1. Clinical Laboratory Parameters

Table 5-6 Safety Laboratory Assessments

Laboratory			
Assessments	·		
Hematology	Platelet count	RBC indices:	WBC count with differential (absolute):
	RBC count	MCV	Neutrophils
	Hemoglobin	MCH	Lymphocytes
	Hematocrit	MCHC	Monocytes
			Eosinophils
			Basophils
Clinical Chemistry ^a	BUN	Potassium	Aspartate aminotransferase (AST)
	Creatinine	Sodium	Alanine aminotransferase (ALT)
	Glucose (fasting ^b) Calcium Alkaline phosphatase		Alkaline phosphatase
	Total protein	Cholesterol	Total, direct and indirect bilirubin
	Albumin	Chloride	
Routine Urinalysis	Specific gravity, pH, glucose, protein, blood, ketones, bilirubin, urobilinogen, nitrite,		
,	leukocyte esterase by dipstick		
	Microscopic examination (if blood or protein is abnormal)		

^a In Stage 1, blood samples will be collected following 10-hour fasting period.

Descriptive statistics for quantitative clinical laboratory values (in SI units) at Screening, Exit visit, and changes from baseline at Exit/Early Termination visit will be presented by cohort and study intervention group for each clinical laboratory assessment.

Clinical laboratory test values will be considered PCS if they meet either the lower-limit or higher-limit PCS criteria listed in Table 6-5. The number and percentage of participants who have at least one PCS post-baseline clinical laboratory values will be tabulated by cohort and study intervention group at Exit visit. The percentages will be calculated based on the denominator of the number of participants with available non-PCS baseline values and at least one post-baseline value and the numerator of the number of participants with non-PCS baseline value and at least one PCS post-baseline-value.

^b Fasting requirement is for Stage 1 only

Safety Statistical Analysis Plan

2012-201-005 [Stage 1]

A supportive listing of participants with postbaseline PCS values will be provided, including the participant number and baseline and postbaseline values, for the safety population. A listing of conversion factors to convert SI units to conventional units will be provided.

Table 5-7 Clinical Laboratory Summaries

Endpoint	Description	Timing	Methodology
PCS values ^a	 Summary by laboratory category, laboratory test, and PCS criteria Participants with baseline PCS values excluded from analysis Parameters and PCS criteria specified in Sections 6.5.2.2 and 6.5.2.1, respectively 	Screening ^b , Exit ^c	PCS descriptives/ Supportive data listing
Descriptives	Summary by laboratory category and laboratory test in SI and /or CV units and analysis visit Parameters specified in Section 6.5.2.2	Screening ^b , Exit ^c	CFB descriptives

^a Participants who report ≥ 1 postbaseline PCS value and all clinical laboratory for those participants will be listed.

5.6.3.2. Potential Hy's Law

Potential Hy's Law criteria will be listed for the Safety Population as follows:

Table 5-8 Potential Hy's Law Summaries

Parameter	Description	Timing	Methodology
Potential Hy's Law within 24-hour window	Postbaseline assessment of the following laboratory parameters based on blood draws collected within a 24-hour period: • ALT or AST ≥ 3 × ULN • TBL ≥ 2 × ULN • ALP < 2 × ULN	Study Intervention Period	Supportive data listing

5.6.3.3. Vital Signs

Descriptive statistics for vital signs (systolic and diastolic blood pressures, pulse rate, weight, respiration rate, and temperature) at Screening, Baseline (Day 1) and changes from baseline values at each visit and at the Exit/Early Termination visit will be presented by cohort and study intervention group.

^b Visit will be used as baseline for change from baseline summaries.

^c Exit: Final or early termination visit.

Safety Statistical Analysis Plan

2012-201-005 [Stage 1]

Vital sign values will be considered PCS if they meet either the lower-limit or higher-limit PCS criteria listed in Table 6-6. The number and percentage of participants who have at least one PCS post-baseline vital sign value will be tabulated by cohort and study intervention group. The percentages will be calculated based on the denominator of the number of participants with available baseline values or non-PCS baseline values (respiratory rate and temperature) and at least one post-baseline value and the numerator of the number of participants with non-PCS baseline value and at least one PCS post-baseline value.

A supportive listing of participants with postbaseline PCS values will be provided, including the participant number and baseline and postbaseline values, for the safety population.

Table 5-9 Vital Signs Summaries

Endpoint	Description	Timing	Methodology
PCS values ^a	Summary by parameter and PCS criteria Denominator: available baseline or non-PCS baseline (respiratory rate or temperature) and at least one end-of-study or postbaseline values Parameters and PCS criteria specified in Sections 6.5.3.2	Blood pressure, pulse rate, temperature: Day 1 ^b , Day 2, Day 8, Exit ^c Respiration rate, weight: Screening ^b , Exit ^c	PCS descriptives/ Supportive data listing ^a
Descriptives	and 6.5.3.1 respectively Summary by parameter and analysis visit Parameters specified in Section 6.5.3.2	Blood pressure, pulse rate, temperature: Screening, Day 1 ^b , Day 2, Day 8, Exit ^c Respiration rate, weight: Screening ^b , Exit ^c	CFB descriptives

^a Participants who report ≥ 1 postbaseline PCS value and all vital signs will be listed.

5.6.3.4. Electrocardiogram

Descriptive statistics for ECG parameters (heart rate, RR interval, PR interval, QRS interval, QT interval, and QTc) at Baseline and Exit/Early Termination visits, and changes from baseline values at Exit/Early Termination visit will be presented by cohort and study intervention group.

The QTc will be calculated using the Fridericia correction (if the vendor does not provide). QTcF are derived as follows:

^b Visit will be used as baseline for change from baseline summaries.

^c Exit: Final or early termination visit.

Safety Statistical Analysis Plan

2012-201-005 [Stage 1]

Table 5-10 Derivations of OTcF

Parameter	Derivation if RR available	Derivation if RR unavailable
QTcF	QT	QT
(QTc Fridericia)	cubic root of RR	cubic root of 60/HR

ECG parameter values will be considered PCS if they meet either the lower-limit or higher-limit PCS criteria listed in Table 6-7. The number and percentage of participants who have at least one PCS post-baseline ECG values will be tabulated for all participants by cohort and study intervention group. The percentages will be calculated based on the denominator of the number of participants with available non-PCS baseline values and at least one post-baseline value and the numerator of the number of participants with non-PCS baseline value and at least one PCS post-baseline value.

A supportive listing of participants with postbaseline PCS values will be provided, including the participant number and baseline and postbaseline values, for the safety population.

Table 5-11 ECG Summaries

Endpoint	Description	Timing	Methodology
PCS values	Summary by parameter and PCS criteria Participants with baseline PCS values excluded from analysis Parameters and PCS criteria specified in Sections 6.5.4.2 and 6.5.4.3, respectively.	Screening ^b , Exit ^c	PCS descriptives/ Supportive data Listing ^a
Descriptives	Summary by parameter and analysis visit Parameters specified in Section 6.5.4.3	Screening ^b , Exit ^c	CFB descriptives

^a Participants who report ≥ 1 postbaseline PCS value and all ECG will be listed.

5.6.3.5. Physical Exam

Abnormalities in PEs during Stage 1 of the study will be captured in medical history or AE data panels. Therefore, there will be no separate analyses for physical examination.

5.6.3.6. Best-corrected Visual Acuity

BCVA will be measured in each eye using the ETDRS chart. Descriptive statistics for BCVA at Screening, Baseline (Day 1), and changes from baseline at each postbaseline visit will be presented by cohort, and study intervention group for each eye. Vision loss will also be

^b Visit will be used as baseline for change from baseline summaries.

^c Exit: Final or early termination visit.

Safety Statistical Analysis Plan

2012-201-005 [Stage 1]

summarized by study intervention group for each eye at each visit in a categorical tabulation as severe (\geq 30 letters decrease from baseline), moderate (\geq 15 and < 30 letters decrease from baseline) and no loss or mild (< 15 letters decrease from baseline).

Table 5-12 BCVA Summaries

Parameter	Description	Timing	Methodology
Vision loss	 Severe vision loss (>= 30 letters decrease from baseline) Moderate vision loss (>= 15 and < 30 letters decrease from baseline) No loss or mild vision loss (<15 letters decrease from baseline) 	Treatment Period	Categorical descriptives
BCVA	Raw values and change from baseline	Treatment Period	CFB descriptives

5.6.3.7. Intraocular Pressure

IOP will be measured in each eye using the Goldmann applanation tonometer. At least 2 measurements will be taken for each eye. If the 2 independent measurements differ by \leq 2 mm Hg, a third measurement is not required, and the 2 measurements will be recorded. If the first 2 measurements differ by > 2 mm Hg, a third measurement must be made, and all 3 measurements will be recorded. The mean of the 2 (or 3) measures will be used as the IOP value. If, for any reason, only a single measurement is obtained, then this measurement will be used as the IOP value.

Descriptive statistics for IOP at Screening, Baseline (Day 1), and changes from baseline and number of participants reporting IOP > 21 mm Hg at each postbaseline visit will be presented by cohort and study intervention group for each eye.

Table 5-13 IOP Summaries

Parameter	Description	Timing	Methodology
IOP category	IOP > 21 mmHg (raw value)	Treatment period	Categorical descriptives
IOP	Raw values and change from baseline	Treatment period	CFB descriptives

